9.4. Sample Collection and Testing

The Schedule of Activities (Section 2) lists the schedule for sample collections in this study.

[Appendix 2](#) lists the clinical laboratory tests that will be performed for this study.

9.4.1. Samples for Study Qualification and Health Monitoring

Blood and urine samples will be collected to determine whether patients meet inclusion/exclusion criteria and to monitor patient health.

Cerebrospinal fluid will be collected in some patients to determine whether patients meet the inclusion criteria, and in other patients as part of the optional LP addendum.

Investigators must document their review of each laboratory safety report.

Samples collected for specified laboratory tests will be destroyed within 60 days of receipt of confirmed test results. Tests are run and confirmed promptly whenever scientifically appropriate. When scientific circumstances warrant, however, it is acceptable to retain samples to batch the tests run, or to retain the samples until the end of the study to confirm that the results are valid. Certain samples may be retained for a longer period, if necessary, to comply with applicable laws, regulations, or laboratory certification standards.

9.4.2. CSF A β and Tau Proteins and Solanezumab

Screening LPs may be performed as part of the study eligibility criteria for patients opting to use CSF A β levels to determine patient eligibility for study participation (Section 0). For these patients, a second LP will be administered at 1 later time point. These patients will be assigned to have the second LP at Week 4, 8, 12, 24, 52, 76, or 104 (or early discontinuation). Specific instructions for the LP procedure itself will be provided in the manual of operations.

The collected CSF will be assayed for measurement of solanezumab, A β species, tau proteins, and storage of CSF for use in future research. The results of CSF analyses will be used to determine whether patients meet inclusion/exclusion criteria and to compare solanezumab and placebo treatment effects. A portion of the collected CSF will be used for central laboratory testing of CSF solanezumab, A β species, and tau proteins. The remainder will be aliquotted and stored for future research where allowed. In countries prohibiting sample storage, it will not be considered a protocol deviation if CSF is not collected for storage and future analysis.

9.4.2.1. Timing of CSF Sampling

Visits when CSF is sampled are shown in the body and footnotes of the Schedule of Activities (Section 2).

9.4.2.2. CSF Collection Procedures

Cerebrospinal fluid will be collected according to the procedure described in [Appendix 3](#). It is critical that for each CSF sample, the date of sample acquisition is accurately recorded.

Sample handling and shipment to the central laboratory will occur per instructions given to the investigative study site.

Samples collected from placebo-treated patients during the double-blind period will not be assayed for solanezumab. Bioanalytical CSF samples collected to measure investigational product concentration will be retained for a maximum of 2 years following last patient visit for the study.

Cerebrospinal fluid samples collected to assess A β species and tau proteins and allow for future research may be stored for a maximum of 15 years following last patient visit for the trial at a facility selected by the sponsor (Section 9.4.6.2).

Results from analysis of screening samples of CSF in regards to patient inclusion eligibility will be reported to investigative sites (that is, eligible or not eligible for inclusion).

Results from analyses of CSF for solanezumab, A β species, and tau proteins to assess treatment effects will not be reported to investigative sites or other blinded personnel at a subject level.

9.4.3. Plasma Samples for Assessment of A β s and Solanezumab

9.4.3.1. Timing of Plasma Sampling

Visits when plasma is sampled and the time of sampling relative to study drug dosing are shown in the body and footnotes of the Schedule of Activities (Section 2). Samples from placebo-treated patients will not be assayed for solanezumab. Amyloid- β peptide or solanezumab concentration results in plasma that could unblind the study will not be reported to investigative sites or other blinded personnel.

9.4.3.2. Plasma Collection Procedures

Venous blood samples will be drawn into sodium ethylenediaminetetraacetic acid tubes for the determination of plasma concentrations of solanezumab and A β peptides at the times indicated in

the Schedule of Activities (Section 2). A saline well or heparin lock may be used to facilitate blood collection.

On the dosing day, the blood will be collected from the arm that did not receive the infusion of study drug.

It is critical that for each blood sample, date and time of sample acquisition and date and time of administration of study drug are accurately recorded. Only plasma samples collected from patients dosed with solanezumab will be assayed for solanezumab.

Sample handling and shipment to the central laboratory will occur per instructions given to the investigative study site.

Bioanalytical samples collected to measure investigational product concentration will be retained for a maximum of 2 years following last patient visit for the study.

The remainder of the plasma not used for the assessment of A β species may be stored for a maximum of 15 years following last patient visit for the study at a facility selected by the sponsor (Section 9.4.6.2).

Results of plasma solanezumab and A β analyses that could unblind the study will not be reported to investigative sites or other blinded personnel at a subject level.

9.4.4. Serum Samples for Anti-Solanezumab Immunogenicity

9.4.4.1. Timing of Blood Sampling

Where local regulations and ethical review boards (ERBs) allow, serum for immunogenicity testing will be prepared from blood drawn at the designated visits and times relative to study drug dosing as indicated in the body and footnotes of the Schedule of Activities (Section 2). Immunogenicity will be assessed by a validated assay designed to detect anti-drug antibodies in the presence of solanezumab. Antibodies may be further characterized and/or evaluated for their ability to neutralize the activity of solanezumab. Serum immunogenicity results and any associated plasma A β peptide and solanezumab drug results used to interpret immunogenicity test results that could unblind the study will not be reported to investigative sites or other blinded personnel.

9.4.4.2. Blood Collection Procedures

It is critical that for each serum sample, date and time of sample acquisition and date and time of administration of study drug are accurately recorded.

Sample handling and shipment to the central laboratory will occur per instructions given to the investigative study site.

Samples will be retained for a maximum of 15 years after the last patient visit for the study, or for a shorter period if regulations and ERBs impose shorter time limits, at a facility selected by the sponsor. The duration allows the sponsor to respond to future regulatory requests related to solanezumab.

9.4.5. Apolipoprotein E Genotyping

Apolipoprotein E (APOE) genotyping is a mandatory part of this study, unless country-specific laws and regulations prohibit this type of testing. Blood sampling for APOE genotyping will be performed as shown in the Schedule of Activities (Section 2). Neither patients nor investigators will receive the genotype results unless there is a country-specific law or regulation that requires notification of the results. Failure to collect samples for APOE will not be considered a protocol deviation if country-specific regulations prohibit the testing of genetic material or transportation of such material outside of the country.

9.4.6. Samples for Biomarker Research

9.4.6.1. Pharmacogenetic Samples

A blood sample will be collected for pharmacogenetic analysis as specified in the Schedule of Activities (Section 2) where local regulations allow.

Samples will not be used to conduct unspecified disease or population genetic research either now or in the future. Samples will be used to investigate variable response to solanezumab and to investigate genetic variants thought to play a role in AD. Assessment of variable response may include evaluation of AEs or differences in efficacy.

All samples will be coded with the patient number. These samples and any data generated can be linked back to the patient only by the investigator site personnel.

Samples will be retained for a maximum of 15 years after the last patient visit for the study, or for a shorter period if local regulations and/or ERBs impose shorter time limits, at a facility selected by the sponsor. This retention period enables use of new technologies, response to regulatory questions, and investigation of variable response that may not be observed until later in drug development or when the drug is commercially available.

Molecular technologies are expected to improve during the 15-year storage period and therefore cannot be specifically named. However, existing approaches include whole genome or exome sequencing, genome wide association studies, candidate gene studies, and epigenetic analyses. Regardless of technology utilized, genotyping data generated will be used only for the specific research scope described in this section.

9.4.6.2. Biomarker Storage Samples

As discussed above, serum, plasma, and CSF samples for non-pharmacogenetic biomarker research will be collected at the times specified in the Schedule of Activities (Section 2) where local regulations allow.

Samples will be used for research on the drug target, disease process, variable response to solanezumab, pathways associated with AD, mechanism of action of solanezumab, and/or research method or in validating diagnostic tools or assay(s) related to AD.

All samples will be coded with the patient number. These samples and any data generated can be linked back to the patient only by the investigator site personnel.

Samples will be retained for a maximum 15 years after the last patient visit for the study, or for a shorter period if local regulations and ERBs impose shorter time limits, at a facility selected by the sponsor. This retention period enables use of new technologies, response to regulatory questions, and investigation of variable response that may not be observed until later in drug development or when the drug is commercially available.

9.5. Health Economics

Refer to Section [9.1.2](#) for description of health economics outcomes.

10. Statistical Considerations and Data Analysis

10.1. Determination of Sample Size

Power and sample size calculations have been based on the analysis of the primary objective using an effect size calculation of treatment difference at the end of the study.

To calculate power, we used an expected decline in ADAS-Cog₁₄ at 2 years of 4.41 points for placebo-treated patients and 3.21 points for solanezumab-treated patients, with a common standard deviation of 8 (Doraiswamy et al. 2014). This is equivalent to a difference of 1.2 points over 2 years, with an effect size = 0.15. Based on these assumptions and a 25% discontinuation rate, 1225 randomized patients per arm (919 completers per arm) or 2450 total randomized patients will have approximately 89% power to detect a significant treatment difference at 2 years using a 2-sided significance level of 0.05.

Patients who are randomized but not administered treatment may be replaced to ensure that enough patients may complete the study.

10.2. General Statistical Considerations

Statistical analysis of this study will be the responsibility of Eli Lilly and Company or its designee.

All analyses will follow the intent-to-treat (ITT) principle unless otherwise specified. An ITT analysis is an analysis of data by the groups to which patients are assigned by random allocation, even if the patient does not take the assigned treatment, does not receive the correct treatment, or otherwise does not follow the protocol. When change from baseline is assessed, patients will be included in the analysis only if both a baseline and a postbaseline measure are available. Unless otherwise defined, a baseline measure is the last non-missing observation collected prior to the first infusion of study medication. Endpoint is the last non-missing postbaseline measurement.

For mixed-effect model repeated measure (MMRM) models, observations collected at nonscheduled visits will not be included in the analyses. For analyses using last observation carried forward, the last non-missing postbaseline observation (scheduled or unscheduled) will be used to calculate change from baseline.

Unless otherwise noted, all tests of treatment effects will be conducted at a 2-sided alpha level of 0.05; 2-sided confidence intervals (CIs) will be displayed with a 95% confidence level. All tests of interactions between treatment and other factors will be conducted at an alpha level of 0.05.

Any change to the data analysis methods described in the protocol will require an amendment ONLY if it changes a principal feature of the protocol. Any other change to the data analysis methods described in the protocol, and the justification for making the change, will be described in the CSR. Additional exploratory analyses of the data will be conducted as deemed appropriate.

Complete details of the statistical methods to be used in this study are contained in the statistical analysis plan (SAP).

10.2.1. Analysis Populations

The primary and secondary efficacy measures will be analyzed using the ITT population. In addition, each of these measures will be analyzed using the per-protocol population and the completer population to verify the robustness of the results. Summaries and analyses for safety measures will be based on the safety population. Tabulation of the number and percentage of patients included in each population will be provided. The SAP contains detailed descriptions for each of these patient populations.

10.2.2. Handling of Missing Items for Scales

If any of the individual items for the ADAS-Cog or ADCS-MCI-ADL are missing or unknown, every effort will be made to obtain the score for the missing item or items.

For ADAS-Cog₁₄, if <30% (4 or fewer of a total of 14) of the items are missing, the total score (maximum = 90) will be imputed as follows: The total from remaining items will be multiplied by a factor that includes the maximum score for the missing items. For example, if the first item, “Word-Recall Task,” which ranges from a score of 0 through 10 (maximum = 10), is missing, and the second item “Commands,” which ranges from a score of 0 to 5 (maximum = 5), is missing, then the multiplication factor = $90 / (90 - [10 + 5]) = 90 / 75 = 1.2$. Thus, the total score for this example will be the sum of the remaining 12 items multiplied by 1.2. The imputed number will be rounded up to the nearest integer. If more than 4 items are missing, the total score for ADAS-Cog₁₄ at that visit will be considered missing.

For the ADCS-MCI-ADL, if <30% of the items are missing, the total score will be imputed. The sum of the nonmissing items will be prorated to the sum of total items. The imputed number will be rounded up to the nearest integer. If the nearest integer is greater than the maximum possible score, the imputed score will be equal to the maximum score. If >30% of the items are missing, the total score for ADCS-iADL at that visit will be considered missing.

The same imputation technique will be applied to the CDR-SB. If only 1 box (of 6) of the CDR is missing, the sum of the boxes will be imputed by prorating the sum from the other 5 boxes. If the score from more than 1 box is not available, the CDR-SB at that visit will be considered missing.

For all other scales, if any item is missing, any total or sum involving that item will be considered missing.

10.2.3. Pooling of Investigators

This study will be conducted by multiple investigators at multiple sites internationally. In the event that a site has an inadequate number of patients (defined as 0 or 1 randomized patient per treatment group) for the planned analyses, the following strategy will be implemented. Data from all such sites within a country will be pooled. If the resulting pool within a country is still inadequate, no further pooling will be performed.

10.3. Treatment Group Comparability

10.3.1. Patient Disposition

A detailed description of patient disposition will be provided at the end of the study. The percentage of patients discontinuing from each treatment group will be compared by reason for discontinuation using Fisher's exact test.

10.3.2. Protocol Deviations

Listings of patients with significant protocol deviations will be provided for the ITT population. The following list of significant protocol deviations will be determined from the clinical database and from the Lilly clinical/medical group:

- Informed consent deviation
- Did not have an assessment of the ADAS-Cog at any of the visits at which the scale was scheduled to be assessed
- Did not have an assessment of the ADCS-MCI-ADL at any of the visits at which the scale was scheduled to be assessed
- Protocol deviations of inclusion/exclusion criteria
- Had a study dosing algorithm deviation (such as if patients randomized to Treatment A were given Treatment B or patients randomized to Treatment A never received the assigned study drug)
- Had unqualified rater or raters with substantial scoring errors for the ADAS-Cog at any time
- Had unqualified rater or raters with substantial scoring errors for the ADCS-MCI-ADL at any time
- Did not have the same study partner(s) throughout the trial
- Greater than or equal to 20% of infusions are incomplete
- Had change in doses of AChEI medication(s) and/or memantine or have started/stopped AChEI medication(s) and/or memantine anytime during the study without consulting the sponsor
- Deviated from the protocol in any other way

10.3.3. Patient Characteristics

The patient's age, gender, race, height, body weight, body mass index (weight (kg) / [height (m)]²), tobacco use, alcohol use, caffeine use, years of education, work status, time since onset of first AD symptoms, time since diagnosis, MMSE at Visit 1, APOE4 carrier status (carrier [$\epsilon 2/\epsilon 4$, $\epsilon 3/\epsilon 4$, $\epsilon 4/\epsilon 4$], noncarrier [$\epsilon 3/\epsilon 3$, $\epsilon 2/\epsilon 2$]), APOE4 genotype ($\epsilon 2/\epsilon 4$, $\epsilon 3/\epsilon 4$, $\epsilon 4/\epsilon 4$, no $\epsilon 4$), having 1 or more first degree relatives with AD, and AChEI and/or memantine use at baseline will be recorded.

Baseline characteristics will be summarized for the ITT and per-protocol populations by treatment group and overall. Summaries will include descriptive statistics for continuous and categorical measures. Fisher's exact test or Pearson's chi-square test will be used for treatment-group comparisons of categorical data. For continuous data, analysis of variance with independent factors for treatment will be used.

10.3.4. Concomitant Therapy

Approved AD medications will be permitted in this study as described in Section 7.8. Patients who begin such treatments during the study will be analyzed as part of the ITT population. Analyses stratified by use of these medications at baseline will be conducted.

10.3.5. Treatment Compliance

The proportion of patients who are significantly noncompliant as noted in Section 7.7 will be summarized and compared among all treatment groups using Fisher's exact test.

10.4. Primary and Secondary Analyses

10.4.1. Primary Analyses

The primary objective of this study is to test the hypothesis that intravenous infusion of solanezumab will slow cognitive decline as compared with placebo in patients with prodromal AD. This will be assessed using an MMRM analysis of the ADAS-Cog₁₄ in patients with prodromal AD at baseline (Visit 1 MoCA score of 17 to 28), in which the specific hypothesis is that the cognitive decline from baseline at the end of the treatment period (104 weeks) for solanezumab will be significantly less than that for placebo.

The change from baseline score on the ADAS-Cog₁₄ at each scheduled postbaseline visit (according to the Study Schedule) during the treatment period will be the dependent variable. The model for the fixed effects will include terms for 7 effects: baseline score, pooled investigator, treatment, visit, treatment-by-visit interaction, concomitant AChEI and/or memantine use at baseline (yes/no), and age at baseline. Visit will be considered a categorical variable with values equal to the visit numbers at which the scales were assessed. The null hypothesis is that the contrast between the solanezumab-treated patients versus placebo-treated patients at the last visit equals zero. An unstructured covariance matrix will be used to model the within-patient variance-covariance errors. If the unstructured covariance structure matrix results in a lack of convergence, the following tests will be used in sequence: heterogeneous Toeplitz covariance structure, heterogeneous autoregressive covariance structure, heterogeneous compound symmetry covariance structure, and compound symmetry covariance structure.

The Kenward-Roger approximation will be used to estimate the denominator degrees of freedom.

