General Considerations. All analyses will follow the intent-to-treat principle unless otherwise specified. When change from baseline is assessed, patients will be included in the analysis only if both a baseline and a postbaseline measure are available. For analyses using last observation carried forward, the last nonmissing postbaseline observation (scheduled or unscheduled) will be used to calculate change from baseline. Unless otherwise noted, all tests of treatment effects will be conducted at a 2-sided alpha level of 0.05; 2-sided confidence intervals will be displayed with a 95% confidence level. All tests of interactions between treatment and other factors will be conducted at an alpha level of 0.05.

Primary Analysis. The primary objective of this study is to test the hypothesis that intravenous infusion of solanezumab will slow cognitive decline as compared with placebo in patients with prodromal AD. This will be assessed using an mixed-effect model repeated measure (MMRM) analysis of the Alzheimer's Disease Assessment Scale–Cognitive subscale (ADAS-Cog₁₄) in patients with prodromal AD at baseline (Visit 1 Montreal Cognitive Assessment [MoCA] score of 17 to 28), in which the specific hypothesis is that the cognitive decline from baseline at the end of the treatment period (104 weeks) for solanezumab will be significantly less than that for placebo. The change from baseline score on the ADAS-Cog₁₄ each scheduled postbaseline visit (according to the Study Schedule) during the treatment period will be the dependent variable. The model for the fixed effects will include terms for 7 effects: baseline score, pooled investigator, treatment, visit, treatment-by-visit interaction, concomitant acetylcholinesterase inhibitor (AChEI) and/or memantine use at baseline (yes/no), and age at baseline. Visit will be considered a categorical variable with values equal to the visit numbers at which the scales were assessed. The null hypothesis is that the contrast between the solanezumab-treated patients versus placebo-treated patients at the last visit equals zero.

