- a If desired, the following visits may take place over 2 consecutive days: Visit 2 (randomization visit), Visit 15 (Week 52), Visit 28 (Week 104), and ED. If done over 2 days, it is recommended that the following procedures be performed on Day 2: CDR-SB, RBANS, NPI, and FCSRT, as applicable. Dosing should occur at the end of the second day.
- b Visits should be scheduled as close as possible to the intended week in relation to baseline. Furthermore, visits must be scheduled such that study drug administration never occurs at intervals of less than 21 days.
- c All patients will have either a florbetapir PET scan or lumbar puncture at screening to determine eligibility. If florbetapir PET scan is used, this procedure will be repeated at the 24-month endpoint (or early discontinuation). If LP is used, then a second LP will be administered at 1 later time point, with LP patients being assigned by the IWRS to have the second LP at Week 4, 8, 12, 24, 52, 76, or 104 (or ED). Opting out of the 2nd LP will not be considered a protocol deviation. Any CSF collected via LP as part of the main study or the optional LP addendum will be analyzed for A β s, tau proteins, solanezumab, and biomarker storage. LPs are to be performed before study drug administration. It will not be considered a protocol deviation if the LP is not performed or if CSF is not collected for storage and future analysis in countries prohibiting sample storage. Patients undergoing LP will have PT/INR, PTT, and platelet count tested prior to each LP.
- d Pharmacokinetic samples should be obtained immediately before dosing at all designated visits. In addition, postdose samples should be taken at Visits 2 and 5.
- e Visit 301 should be scheduled to occur 4 months after last dose (that is, 3 months after Visit 28 or in case of ED, 4 months after last dose).

3. Introduction

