5.1. Overview of Study Design

Study H8A-MC-LZBE (LZBE) is a multicenter, randomized, double-blind, parallel, placebo-controlled Phase 3 trial comparing solanezumab with placebo for 24 months in approximately 2450 patients with prodromal AD. Patients who meet entry criteria will be randomized in a 1:1 ratio to receive an infusion of solanezumab 400 mg or placebo once every 4 weeks. Patients will be randomized by site and by use of florbetapir PET scanning or CSF for study eligibility (Section 6.1). The primary hypothesis being tested in Study LZBE is that solanezumab will slow the clinical progression of AD as compared with placebo in patients with prodromal AD.

In addition, participants in the ^{18}F -AV-1451 tau imaging addendum will be included in an interim analysis (Section 10.8) designed to assess the relationship between ^{18}F -AV-1451 tau PET and solanezumab treatment.

Three months after the end of the double-blind treatment period (or 4 months after the last dose in case of early discontinuation), patients will come to a follow-up visit for biomarker and safety assessments.

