6.1. Inclusion Criteria

Patients are eligible to be included in the study only if they meet all of the following criteria at screening:

Patient Characteristics and Diagnostic Criteria

- [1] Is aged 55-85 years
- [2] Has a diagnosis by the study investigator of a clinical syndrome of cognitive impairment consistent with prodromal AD per IWG diagnostic criteria or MCI due to AD per NIA-AA diagnostic criteria, confirmed by all of the following:
 - a. Subjective cognitive complaint or informant report of cognitive impairment for at least 6 months prior to Visit 1
 - b. No significant impairment of iADLs by patient and informant report and in the judgment of the investigator (that is, patients are maintaining their independence of functioning in daily life with minimal aids or assistance)
 - c. Not demented, based on IWG or NIA-AA guideline criteria
- [3] Scores 17-28 on Montreal Cognitive Assessment (MoCA) at Visit 1
- [4] Scores <27 on free recall cutoff score from the Free and Cued Selective Reminding Test (FCSRT) (Picture version) at Visit 1
- [5] Scores ≤ 4 on Modified Hachinski Ischemia Scale
- [6] Scores >0 on the Functional Activities Questionnaire (FAQ)
- [7] Has a reliable study partner who is in frequent contact with the patient (defined as at least 10 hours per week), will accompany the patient to the study visits, and will be available by telephone at designated times

Note: Study partners must be able to communicate with site personnel and be willing to comply with protocol requirements, and in the investigator's opinion must have adequate literacy to complete the protocol-specified questionnaires. Study partners must come in person to all visits with assessments that require their input.

- [8] Has a florbetapir PET scan or CSF result at screening consistent with the presence of amyloid pathology (see also Exclusion Criterion [34]). (Note: Previously acquired amyloid PET scans unrelated to Study LZBE may be permitted for use in meeting this criterion. Refer to specific guidance in the manual of operations.)

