7.2. Method of Treatment Assignment

Patients who meet all criteria for enrollment will be randomized to double-blind treatment at Visit 2. Assignment to treatment groups will be determined by a computer-generated random sequence using an interactive web-response system (IWRS). The IWRS will be used to assign a vial containing double-blind investigational product to each patient. Site personnel will confirm that they have located the correct vial by entering a confirmation number found on the vial into the IWRS.

To achieve between-group comparability, the randomization will be stratified by site and by use of florbetapir PET scanning or CSF for study eligibility.

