10.4.2. Secondary Analyses

10.4.2.1. Clinical Outcomes

Similar to the primary analysis, each of the secondary efficacy outcomes will be assessed using an MMRM analysis. These secondary efficacy outcomes include ADCS-MCI-ADL, MMSE, MoCA, CDR-SB, NPI, RUD-Lite, EQ-5D Proxy, QoL-AD patient and proxy, RBANS, and FAQ. For each secondary efficacy measure, the change from baseline score at each scheduled postbaseline visit (according to the Study Schedule) during the treatment period will be analyzed using the same MMRM model described for the primary analysis.

An additional MMRM analysis, termed a slopes analysis, will be conducted examining the change from baseline score on the ADAS-Cog₁₄, ADCS-MCI-ADL, CDR-SB, FAQ, MMSE, and MoCA at each scheduled postbaseline visit. In contrast to the primary analyses, which considered visit (time) as a categorical variable, time from randomization will be treated as a continuous variable. The model for the fixed effects will include baseline score, pooled investigator, treatment, time, treatment-by-time interaction, concomitant AChEI and/or memantine use at baseline (yes/no), and age at baseline. The treatment-by-time interaction term will be examined to assess whether solanezumab and placebo have differing slopes in terms of cognitive or functional progression. The effect of a quadratic term for time (and its associated interaction with treatment) on the model will also be examined.

Categorical analyses of slowing cognitive and functional decline will be conducted comparing proportions of patients reaching certain levels of decline between solanezumab and placebo. The precise definitions of cognitive and functional decline and analysis methods will be detailed in the SAP prior to database lock.

Any additional analyses of secondary efficacy outcomes will be specified in the SAP prior to database lock.

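### Minor: the primary MMRM omits florbetapir PET versus CSF, one of the two factors used to stratify randomization, and gives no reason

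*Protocol*

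**What the plan says.** Protocol section 7.2 gives the randomization scheme: "To achieve between-group comparability, the randomization will be stratified by site and by use of florbetapir PET scanning or CSF for study eligibility". Protocol section 5.1 and SAP sections 5.1 and 5.3 name the same two factors. The second factor is defined for everyone, since footnote c to the Schedule of Activities states: "All patients will have either a florbetapir PET scan or lumbar puncture at screening to determine eligibility".

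The primary model is in Protocol section 10.4.1, and the synopsis repeats it: "The model for the fixed effects will include terms for 7 effects: baseline score, pooled investigator, treatment, visit, treatment-by-visit interaction". The remaining two of the seven effects are AChEI and/or memantine use at baseline and age at baseline. Site is represented by pooled investigator, with small sites combined as section 10.2.3 describes: "Data from all such sites within a country will be pooled". PET/CSF is not among the seven.

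In section 10.4.2.1 each secondary outcome "will be analyzed using the same MMRM model described for the primary analysis", so the omission carries over. The slopes model there has its own list, which also lacks the stratum. The SAP contains no efficacy model, so it neither adds the factor nor explains its absence.

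**The concern.** The sponsor judged the eligibility route worth balancing by design, then analysed as if that balance had not been imposed. One stratification factor is in the model and the other is not, and the reader cannot tell whether this was decided or overlooked.

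If the route predicts decline, stratifying on it reduces the true variance of the treatment contrast. A model without the term leaves that between-stratum variance in its residual. It then reports too wide a standard error and rejects less often than it should. What is at stake is a little precision the design has already paid for. The treatment estimate is not biased, and the type I error can only fall below nominal.

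**Working it through.** **Inputs.** From Protocol section 10.1: difference 1.2 points (4.41 − 3.21), SD 8, 919 completers per arm (1225 × 0.75 = 918.75), two-sided 0.05. The documents do not give the CSF share *p* or the PET–CSF gap *D* in 2-year change. Both are assumed: *p* from 0.2 to 0.5 and *D* from 1 to 3 points.

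**Stated power.** SE = 8 × √(2/919) = 0.3732. Then 1.2/0.3732 = 3.215, and Φ(3.215 − 1.960) = Φ(1.255) = 89.5%. This agrees with the stated figure of about 89%. It is a plain two-group calculation without covariates, so the omission does not undermine it.

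**With and without the stratum**, taking it as balanced between arms:

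- Share of Week 104 variance explained: R² = p(1 − p)D²/64.
- True SE = 0.3732 × √(1 − R²).
- Term omitted: the test uses 0.3732 although the true SE is smaller. Power = Φ(1.255/√(1 − R²)); size = 2[1 − Φ(1.960/√(1 − R²))].
- Term included: power = Φ(1.2/true SE − 1.960).

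| p, D | R² | True SE | Size if omitted | Power omitted | Power included | Gain (points) |
|---|---|---|---|---|---|---|
| 0.2, 1 | 0.0025 | 0.3727 | 0.0497 | 89.56% | 89.61% | 0.04 |
| 0.3, 2 | 0.0131 | 0.3707 | 0.0485 | 89.68% | 89.92% | 0.23 |
| 0.5, 3 | 0.0352 | 0.3666 | 0.0460 | 89.94% | 90.55% | 0.61 |

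**In patients.** For the model without the term to reach the power of the model with it, it needs 1.4, 7.4 or 20.0 more completers per arm. In total that is 2.8, 14.8 or 40.0 completers. Dividing by 0.75 gives 3.7, 19.7 or 53.3 randomized.

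**If pooled investigator already absorbs half of the stratum variance**, R² halves and the gain falls to 0.02, 0.12 or 0.31 points.

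**If the gap is zero**, estimating the term multiplies the Week 104 variance by about 1 + 1/(1838 − 3), a loss of 0.016 points.

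**Simulation with site in the model** (assumed: 150 sites as fixed effects, blocks of 4 within site-by-method cells, 1838 completers, 20,000 runs; Monte Carlo SE in brackets):

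| Setting | p = 0.3, D = 2 | p = 0.5, D = 3 |
|---|---|---|
| Gain in points | 0.35 (0.06) | 0.64 (0.07) |
| Gain if sites mostly use one method (site-level correlation 0.5) | 0.22 (0.06) | 0.25 (0.07) |

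With no gap the simulated change is −0.02 (0.02).

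**Main effect or interaction with visit.** The test is at Week 104. A main effect alone recovers the whole gain if the gap is the same at every visit. If the gap grows linearly from baseline, a main effect removes only 0.21–0.52 of the between-stratum variance at Week 104, and the gain is about 0.01–0.3 points. That calculation assumes a random-slope covariance over the eight postbaseline ADAS-Cog14 visits, scaled to SD 8 at Week 104.

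**The case against.** The strongest reply is that nothing here is an error. Neither document promises to adjust for every stratification factor, and randomization delivers balance with or without a model term. No passage shows the eligibility route to be prognostic: inclusion criterion 8 treats PET and CSF as two ways to establish the same thing ("Has a florbetapir PET scan or CSF result at screening consistent with the presence of amyloid pathology"). The benefit is therefore assumed, and the largest figure needs an even split and a 3-point gap, 2.5 times the planned 1.2-point drug effect. All of this is right, and it is why the point is minor. It does not show the omission to be the better choice, because including the term costs almost nothing even when it is useless.

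The closed-form and simulated gains also differ: 0.23 against 0.35 points in the middle case, about two Monte Carlo standard errors. The closed form leaves site out and assumes exact balance of the stratum among completers. With no balance at all, the middle-case gain would be 89.92% − 89.53%, about 0.38 points, and the simulated value lies between the two. The second decimal should not be relied on, but every simulated and closed-form gain is below one point.

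Criterion 8 also allows some previously acquired amyloid PET scans, so the two categories are not quite as clean as footnote c suggests. This is settled by analysing each patient in the stratum used at randomization.

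Finally, Protocol section 10.2 defers full statistical detail to the SAP, and SAP section 6.1 states that no efficacy objective will be analysed. The SAP's silence is therefore no evidence of carelessness, and no reported result can change. The point bears on the protocol's stated analysis and on any later protocol that reuses its text.

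**Conclusion.** The point holds and is minor. One of the two randomization strata is missing from the primary MMRM, from the secondary models that copy it, and from the slopes model, without explanation. There is no bias, no type I error inflation and no loss against the stated power.

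Over the assumed range of 20–50% CSF and a 1–3 point gap, the unadjusted test runs at 0.050 down to 0.046 and gives up 0.04 to 0.6 points of power. In the middle case (30% CSF, 2 points) the loss is 0.23 points, about 20 randomized patients. These sizes rest entirely on the assumed share and gap. If PET and CSF patients decline alike, nothing is lost by leaving the stratum out.

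**What to change.** In Protocol section 10.4.1 and the matching synopsis paragraph, add the amyloid-confirmation stratum (florbetapir PET versus CSF, as used at randomization) as a fixed effect, together with its interaction with visit. The interaction is preferable because the hypothesis concerns the last visit and a gap in decline is likely to widen over time. Change the count of effects to match. The secondary MMRMs take up the change through their reference to the primary model. The slopes model has its own list and needs the stratum and its interaction with time added separately.

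The cost is about 8 degrees of freedom, 1 for the stratum and 7 for its interaction over eight postbaseline ADAS-Cog14 visits, against about 2450 planned patients. The factor is already recorded for stratification, so no new data are needed. The choice should be written down before unblinding.
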